### 8.2 Best Corrected Visual Acuity by ETDRS Protocol

The BCVA score or visual acuity score using the Early Treatment of Diabetic Retinopathy Study (ETDRS) protocol will be determined for each subject in each eye at each visit. The observed visual acuity score in the study eye will be used for the analyses.

Descriptive statistics for visual acuity score as well as for change from baseline in visual acuity score will be presented for each visit up to the Week 52 visit and at the end of study visit by cohort, overall and for subgroups (defined in Section 4.4).

Number and percentage of subjects with a 5, 10 or 15 letter gain or loss at each visit up to the Week 52 visit and at the end of study visit will also be included by cohort and overall. Number and percentage of subjects with visual acuity preservation (ie, not meeting visual acuity failure criteria as defined below) over 52 weeks will also be included overall and for subgroups (defined in Section 4.4).

Visual acuity failure is defined as having a  $\geq 15$  letter loss at Week 39 or Week 52 confirmed at the next visit excluding visits occurring post-SOC. Additional details are provided below:

- A  $\geq 15$  letter loss at Week 39 and confirmed at Week 52 (or at the next visit after Week 52 with non-missing data [regardless of the visit windowing algorithm as described in Section 4.1.2] if the subject's visual acuity data is missing at the Week 52 visit or the Week 52 visit did not occur). The data after a subject receives standard of care (SOC) is excluded (i.e., censored) from determination

Confidential

of visual acuity failure. If there is no subsequent confirmatory visit data is available after Week 39 then the subject is counted as a visual acuity failure.

- If the subject does not meet the  $\geq 15$  letter loss criterion at Week 39 but does meet the  $\geq 15$  letter loss criterion at Week 52, then the subject's next visit after Week 52 with non-missing data (regardless of the visit windowing algorithm as described in Section 4.1.2) will be the confirmatory visit (i.e., the subject will be counted as a visual acuity failure if the subject's confirmatory visit also is a  $\geq 15$  letter loss). The data after a subject receives standard of care (SOC) is excluded (i.e., censored) from determination of visual acuity failure. If there is no subsequent confirmatory visit data is available after Week 52 then the subject is counted as failure.

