- If SOC occurs before Week 39, the subject's 2 most recent visits available before SOC (with non-missing visual acuity data), regardless of the visit windowing algorithm as described in Section 4.1.2, will be used. If both visit assessments indicate the loss is  $\geq 15$  letters at this visit the subject will be counted as a visual acuity failure, otherwise the subject will not be counted as a visual acuity failure.
- If both Week 39 and Week 52 visits are missing, the subject's 2 most recent visits before Week 39 (and before receiving SOC), regardless of the visit windowing algorithm as described in Section 4.1.2, with non-missing values will be used. If both visit assessments indicate the loss is  $\geq 15$  letters the subject will be counted as a visual acuity failure, otherwise the subject will not be counted as a visual acuity failure.
- If a subject does not have any post-treatment visual acuity data, the subject will not be counted as a visual acuity failure.

An additional summary of the following two tables including just site 009 (i.e., the site excluded from the Efficacy Evaluable Population) will be performed:

- Summary of Best Corrected Visual Acuity (ETDRS Letters) and Change from Baseline by Visit
- Number and percentage of subjects with visual acuity preservation (i.e., as defined above)

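### The visual acuity preservation rule can count a subject with no usable Week 52 value as preserved although available pre-SOC visits outside the windows show sustained loss, while a later visit without loss can cancel a failure

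*SAP*

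**What the plan says.** SAP 8.2 reports, overall and by subgroup, the subjects with "visual acuity preservation (ie, not meeting visual acuity failure criteria as defined below) over 52 weeks". Failure is a loss of at least 15 letters at Week 39 or Week 52, "confirmed at the next visit excluding visits occurring post-SOC". Five bullets add detail:

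- **Week 39 loss.** Week 52 confirms it. If Week 52 acuity is missing, confirmation comes "at the next visit after Week 52 with non-missing data", with the visit windows set aside. Without any such visit: "If there is no subsequent confirmatory visit data is available after Week 39 then the subject is counted as a visual acuity failure".
- **Week 52 loss, none at Week 39.** The next non-missing visit confirms it, again with the windows set aside. "If there is no subsequent confirmatory visit data is available after Week 52 then the subject is counted as failure".
- **SOC before Week 39.** The last two visits before SOC decide.
- **"If both Week 39 and Week 52 visits are missing".** The last two non-missing visits before Week 39 and before SOC decide, and both must show the loss.
- **No post-treatment acuity.** Not a failure.

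SAP 4.1.2 allows an unscheduled or early withdrawal visit to replace a missed visit only inside that visit's window. SAP 11.2 sets the windows at Days 246 to 302 for Week 39 and Days 337 to 393 for Week 52.

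**The concern.** The bullets use acuity from outside the windows to check a loss already seen at Week 39 or Week 52, but not to detect a loss when Week 52 was missed. Two situations are exposed. With no loss at Week 39 and Week 52 missing, no bullet applies and the subject is preserved under the general definition. With both visits missing, the rule goes back to before Week 39 even when newer pre-SOC acuity exists.

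Retained vision is central to the case for the product (Protocol 4.6), and the preservation rate is reported for small subgroups, one of them defined by high risk of vision loss (SAP 4.4). A subject with documented, confirmed loss close to Week 52 could be labelled preserved. No listed preservation analysis would show it: SAP 8.3 and the table list in SAP 11.3.1 contain no version of the endpoint that varies the handling of a missing Week 52.

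**Working it through.** The SAP gives no figure for this endpoint, so there is none to reproduce. The check is an enumeration of the rule in SAP 8.2 for subjects without SOC.

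**Inputs.** L = loss of at least 15 letters, N = no such loss, M = missing. Week 39 and Week 52 each take L, N or M. Each of the two visits before Week 39 takes L or N. That gives 3 × 3 × 2 × 2 = 36 patterns. Each is crossed with the first visit after Week 52: none, L or N.

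**Assumptions.** N at Week 39 with Week 52 missing falls under the general definition (not a failure). Week 39 missing with a Week 52 loss is read under the Week 52 bullet.

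| Week 39 | Week 52 | No later visit | Later loss | Later visit without loss |
|---|---|---|---|---|
| L | L | failure | failure | failure |
| L | N | preserved | preserved | preserved |
| L | M | failure | failure | preserved |
| N | L | failure | failure | preserved |
| N | N | preserved | preserved | preserved |
| N | M | preserved | preserved | preserved |
| M | L | failure | failure | preserved |
| M | N | preserved | preserved | preserved |
| M | M | earlier visits decide | same | same |

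Each row stands for four patterns of the two earlier visits.

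**Effect of a visit after Week 52, compared with none.** A later loss creates a failure in 0 of 36 patterns. A later visit without loss removes one in 3 rows × 4 = 12 of 36.

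**Week 52 missing and loss afterwards.** There are 3 × 4 = 12 patterns:

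- Week 39 loss: failure in 4 of 4.
- Week 39 without loss: preserved in 4 of 4.
- Week 39 missing: failure in 1 of 4 (both earlier visits show loss), preserved in 3 of 4.

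In total 5 give failure and 7 give preserved. These are counts of patterns, not probabilities.

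**Days 303 to 336.** Week 39 ends on Day 302 and Week 52 starts on Day 337. A visit in between can replace neither, and neither exposed situation reads it. Such visits can exist by design. Protocol Appendix 4 schedules BCVA 26 weeks (26 × 7 = 182 days) after the last Cycle 2 treatment. If that treatment falls between Day 303 − 182 = 121 and Day 336 − 182 = 154, the nominal visit date lies in the gap.

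**Size per subject.** 1/60 = 1.7 points at the planned total; 1/15 = 6.7 points in a group of 15. Fifteen is the maximum of Cohort 12 and serves only as an example, since the subgroup sizes are not in the documents.

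**The case against.** The strongest objection is the time frame. The endpoint covers 52 weeks, so a loss first seen at Week 78 or Week 104 need not count. This stands for loss that truly arose later, and it is why the changed rule belongs at least in a sensitivity analysis. It does not answer the whole point: Days 303 to 336 lie inside the 52 weeks, and the SAP itself goes past Week 52 without a window limit when a later visit may cancel a loss.

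A reader might infer that the one-way effect of later visits is a bias towards the product. The documents do not support that. An unconfirmed loss at Week 39 or Week 52 already counts as failure, so from that cautious start a confirmatory visit can only uphold or remove it. Nor is the rule for two missing visits one-sided: it ignores later recovery as well as later loss, and nothing shows that the older acuity is the better one.

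Other points limit the reach. Unscheduled visits inside the windows replace missed ones. Because of early termination, the final analysis follows the Week 52 visit (SAP 4.2), so some subjects may have no later acuity. Late loss can also appear in the letter-loss table at the end of study visit and in Listing 16.2.3. That table is a per-visit count without confirmation, however, and does not correct the preservation rate. The study is descriptive and its primary objective is safety, which lowers the stakes but does not settle the classification.

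**Conclusion.** The concern holds in a limited form. A subject with Week 52 missing is counted as preserved despite sustained pre-SOC loss outside the windows if Week 39 shows no loss, or if Week 39 is also missing and the two earlier visits do not both show it. A reader might infer that anyone who misses Week 52 and loses vision later counts as preserved. That is not so: with a loss at Week 39, the later loss confirms failure.

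A reader might also take the SAP v5.0 change, made after the first database lock and touching the case where both visits lack data, as a sign that the rule was shaped by results. The SAP gives consistency with the overall definition as its reason, and nothing in the documents shows otherwise.

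The size is 1.7 points per subject at N = 60 and 6.7 points at n = 15. The number of such subjects is not in the documents and may be zero. The conclusion rests on the two reading assumptions in the working. The rule should still be changed, because following it as written can mislabel a confirmed loss near Week 52 and no planned preservation analysis would reveal it.

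**What to change.** Add to SAP 8.2: if Week 52 acuity is missing and Week 39 does not show the loss, the non-missing pre-SOC visit after the Week 39 window (from Day 303) closest to Day 365 stands in for Week 52; a loss of at least 15 letters there is a failure if the next non-missing pre-SOC visit confirms it. Use the look-back to the two visits before Week 39 only when Week 39 is also missing and no later pre-SOC acuity exists. Leave the rule for a Week 39 loss as it is.

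Requiring confirmation keeps a single Week 104 reading from becoming a 52-week failure. Since the SAP otherwise treats an unconfirmed loss as failure, list subjects with an unconfirmed stand-in loss separately.

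Report this at least as a sensitivity version of Tables 14.2.2.3 and 14.2.2.5, with the number of subjects reclassified in each direction and the study day of each stand-in visit.

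The cost is SAP wording and a rerun of two tables on existing data. The drawback is that a loss arising after Week 52 may be counted in a few subjects, and the preservation rate may fall slightly. The study days let the reader judge this.

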If subjects are discharged during daylight hours, appropriate sun protection, e.g., sunglasses and a hat, will be required.

Study subjects will be required to return for an ocular examination 24 hours ± 4 hours following intravitreal administration, followed by 11 visits (Day 8, Day 15, Day 29, Week 6, Week 8, Week 12, Week 26, Week 39, Week 52, Week 78, and Week 104). At these visits, subjects will be monitored with systemic and ophthalmic assessments. In addition, subjects in both the 2 and 3 repeat Light-activated AU-011 administration cohorts will have an additional safety visit on Day 9. Subjects in the 3 repeat Light-activated AU-011 administration cohort will have an additional safety visit at Day 16. Subjects in the observation cohort (Cohort 10) will be seen every 3 months (ie, 90 day (+/- 7 days) intervals from the Screening Visit) until tumor growth is established and then seen at the schedule described in Section 10 and Appendix 1 until the time of receiving Cycle 2, when they will then follow the schedule described in Appendix 4. Subjects in the observation cohort in whom tumor growth is not observed during the 2 year study period will exit the study at Week 104. Subjects in the repeat cycle of AU-011 cohorts (Cohorts 11 and 12) will also follow the schedule described in Section 10 and Appendix 1 until the time they receive the second cycle of AU-011, when they will then follow the schedule described in Appendix 4.

If the second cycle of AU-011 occurs after Visit 15 (Week 78), subjects will be followed for 26 weeks post-treatment and then may be rolled into the long-term follow-up study pending subject consent. Details regarding the follow-up visit schedule after the second cycle of AU-011 can be found in Appendix 4.

All subjects' study participation will be for a minimum of 2 years and all subjects in this study may then be rolled into the long-term follow-up study pending consent.

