Appendix 1 and the sections below describe the procedures that will be performed at each visit.

Additionally, for the observation cohort visits every 3 months (ie, 90 day (+/- 7 days) intervals from the Screening Visit), which occur prior to evidence of tumor growth, the same procedures outlined for Visit 6 (Day 15) will be performed with the exception of OCTA and Anti-drug Antibody (ADA) testing which is not required.

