## 4.3 Definition of Populations

### 4.3.1 Intention-To-Treat Population

The Intention-To-Treat (ITT) population will consist of all enrolled subjects, whether or not they receive one administration of study treatment.

This is the primary population for the efficacy analysis.

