#### 4.6 Calculated Variables

- Study day 1 is defined as the day when first study treatment was received.
- The baseline is defined as the last assessment done before or on study day 1. For instance, if data was collected at screening and Day 1, then the Day 1 value will be used for baseline
- Time since diagnosis of CM (months) = (month and year of screening – month and year of diagnosis).

Assessments done on the date of study treatment administration are assumed to take place before the administration, unless specified otherwise.

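### Any Cohort 10 subject never treated by the analysis is scored as vision-preserved in the overall ITT rate, whatever acuity was measured

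*SAP*

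**What the plan says.** SAP 8.2 introduces the endpoint, a count and a proportion, in these words: "visual acuity preservation (ie, not meeting visual acuity failure criteria as defined below) over 52 weeks will also be included overall and for subgroups". Preservation is thus whatever remains once failures are removed. A failure is a loss of 15 letters or more at Week 39 or Week 52, confirmed at the next visit, with further bullets for missing visits and for standard of care. The last bullet reads: "If a subject does not have any post-treatment visual acuity data, the subject will not be counted as a visual acuity failure".

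Table 14.2.2.3 (SAP 11.3.1) presents this on the ITT population, which SAP 4.3.1 defines as "all enrolled subjects, whether or not they receive one administration of study treatment".

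Under Protocol 6.1, about six subjects without documented growth enter Cohort 10 and are treated only once growth is established. Of those whose tumours do not grow it says: "Subjects in the observation cohort in whom tumor growth is not observed during the 2 year study period will exit the study at Week 104". Until growth they are seen every 90 days, counted from the Screening Visit. Protocol 10.1.1 states that at those visits "the same procedures outlined for Visit 6 (Day 15) will be performed", apart from OCTA and antibody testing. The Visit 6 list in Protocol 10.1.7 includes acuity in both eyes.

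SAP 4.6 sets the time origin: "Study day 1 is defined as the day when first study treatment was received". It fixes the reference value by that same day: "The baseline is defined as the last assessment done before or on study day 1". SAP 11.2 counts the Week 39 window (days 246 to 302) and the Week 52 window (days 337 to 393) from Day 1.

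**The concern.** A subject never given AU-011 provides no evidence about vision after AU-011. Under these definitions such a subject nevertheless adds one to both the numerator and the denominator of the overall preservation rate. The acuity recorded during observation cannot alter that score, because none of it is post-treatment and no change from baseline is defined for it.

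The direction also sits oddly with the rest of SAP 8.2, which is strict where data are incomplete. For a loss of 15 letters or more at Week 39 it says: "If there is no subsequent confirmatory visit data is available after Week 39 then the subject is counted as a visual acuity failure". The subject with no usable data is instead credited as a success.

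At stake is the overall row of the preservation table. It would be read as a rate after treatment while containing subjects whose result was fixed in advance.

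**Working it through.** **Reproduction.** The plan states no preservation rate, power or sample size calculation, so there is no figure to reproduce. The check is a trace of the definitions, followed by the size of the effect.

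**Trace for an enrolled Cohort 10 subject who is never treated**

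1. The subject is enrolled, so is in ITT (SAP 4.3.1) and in Table 14.2.2.3.
2. There is no first treatment, so there is no study day 1 and no baseline (SAP 4.6).
3. Without Day 1, no visit falls in the Week 39 or Week 52 window (SAP 11.2). Without a baseline, no letter loss can be computed.
4. There is no post-treatment acuity, so the last bullet of SAP 8.2 applies and the subject is not a failure.
5. Not a failure means preserved.

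SAP 4.8 generally leaves subjects with missing data out of percentages, but only where nothing else is specified. SAP 8.2 specifies something else, so 4.8 does not stop step 4. The Efficacy Evaluable population (SAP 4.3.2) removes only site 009, and no analysis in SAP 8.3 restricts preservation to treated subjects.

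**Inputs for the size**

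- N = 60, the planned total (SAP 3.3).
- k = number never treated. Not given; taken from 0 to 6, six being roughly the planned size of Cohort 10.
- p = preservation rate among the treated. Not given; assumed to be 50% to 90%.

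**Formula.** Rate as written = [p(N − k) + k]/N = p + (k/N)(1 − p). The treated-only rate is p, so the shift is (k/N)(1 − p).

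| k | k/N | shift at p = 50% | shift at p = 90% |
|---|---|---|---|
| 0 | 0% | 0 | 0 |
| 1 | 1.67% | 1.67 × 0.5 = 0.8 points | 1.67 × 0.1 = 0.2 points |
| 3 | 5.0% | 5.0 × 0.5 = 2.5 points | 5.0 × 0.1 = 0.5 points |
| 6 | 10.0% | 10.0 × 0.5 = 5.0 points | 10.0 × 0.1 = 1.0 point |

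**Check with whole subjects.** Take 54 treated, 11 of them failures, and 6 never treated. Treated-only: 43/54 = 79.6%. As written: (43 + 6)/60 = 49/60 = 81.7%. The difference is 2.0 points, and (6/60)(1 − 0.796) = 2.0 points.

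**Subgroups.** All four subgroups in SAP 4.4 require tumour growth. Cohort 10 enrols subjects without documented growth and treats those who grow, so its never-treated members should fall outside all four.

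**The case against.** The strongest reply is that the effect may not exist. No document says that any Cohort 10 subject stayed untreated. The cohort was small and was closed to enrolment after protocol revision 11, and its subjects are treated once growth is established. This stands: k may be zero. It is not far-fetched that k exceeds zero, however. The protocol provides for untreated exit, and SAP 4.2 brings the final analysis forward to Week 52, so some subjects could still be under observation then.

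Second, the treated-only rate can largely be recovered. SAP 5.1 reports the number treated by cohort and overall, and in the example (49 − 6)/(60 − 6) returns 43/54. Individual acuity is in Listing 16.2.3. This also stands, but it leaves the reader to correct a headline percentage by hand.

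Third, the bullet for subjects missing both Week 39 and Week 52 uses the two most recent earlier visits regardless of windowing, and might be read to reach the observation visits. That reading needs a Week 39 and a baseline, which these subjects lack. If it was intended, the SAP must supply both and say which bullet takes precedence.

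Fourth, the study is descriptive, and the overall row mixes regimens from a single 20 µg dose to two cycles of 80 µg. That limits the importance of the error without making the row correct.

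Stronger readings are tempting but unsupported:

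- **That the plan conceals actual vision loss.** Nothing shows that any untreated subject lost letters.
- **That untreated subjects are also imputed as stable disease.** The baseline-carried-forward rule in SAP 8.1.1 needs a baseline, so their tumour response is undefined rather than favourable.
- **That the same leniency materially affects treated subjects.** Acuity is due on Day 2 and at every visit, and early terminators are asked for a full assessment, so very few treated subjects should have no data.

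**Conclusion.** The point holds in conditional form. As written, SAP 8.2 scores every never-treated ITT subject as preserved in the overall row regardless of measured acuity. Relative to a treated-only rate, the bias can only be upward. With N = 60 and p assumed between 50% and 90%, it is 0.8 to 0.2 points for one such subject and at most 5.0 to 1.0 points for six. The six-subject case needs full Cohort 10 enrolment with nobody treated. With no such subjects it is zero. The growth-based subgroups should be unaffected. This is a modest error in a descriptive rate, but it follows from a stated rule rather than from missing detail, and it is easily removed.

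**What to change.** - Compute the overall preservation rate, and the Cohort 9 to 12 subtotal if it is shown for this endpoint, on subjects given AU-011 at least once. SAP 4.3.3 already has that definition in the Safety population.
- Put never-treated subjects on a separate line, scored from the Screening Visit, which the protocol already uses to time their visits.
- Keep the ITT version as a sensitivity analysis.
- For treated subjects with no post-treatment acuity or no post-baseline tumour data, report how many there are. Use missing-as-failure only as a sensitivity analysis, since it is itself an imputation in the opposite direction.

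The cost is a wording change in the SAP, an extra line in the table and minor programming on data already collected. The overall rate may come out slightly lower.

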### 8.3 Sensitivity Analyses

The following sensitivity analyses will be performed:

- The maximum tumor thickness and largest basal diameter endpoints (i.e., as described in Sections 8.1.5 and 8.1.6, respectively) will be summarized on ITT population excluding post-standard of care data (i.e. all data after receiving standard of care will be excluded for the standard of care subjects).
- BCVA data (Section 8.2) will be summarized on ITT population excluding post-standard of care data. Number and percentage of subjects with a 5, 10 or 15 letter gain or loss at each visit up to the Week 52 visit and at the end of study visit will also be provided for: 1) Efficacy Evaluable population; 2) Efficacy Evaluable population excluding post-standard of care data.
- Tumor response (section 8.1.7) will be summarized on Efficacy Evaluable population.

